Level two allocation involves the randomisation of young people to RBT or BAU. This will be conducted by research staff, using a secure, on-line randomisation service (Sealed Envelope Ltd). after informed consent has been taken and the baseline assessment completed and before any trauma screening has been conducted. The allocation will involve an equal probability of receiving RBT or BAU and will employ random permuted blocks of variable size (4, 6 or 8) with a random block seeded throughout. Randomisation will be conducted by research staff using a secure, independent randomisation service, Sealed Envelope Ltd. Randomisation will be stratified by service (youth justice, edge of care, youth development, early help, children's services), sex (male, female), and age group (<15 years, 15 years or more). Stratification variables have been chosen to ensure allocation is balanced across services, sex, and age as some workers specialise in working with older or younger males and females. A full quality assurance AUDIT trail will be kept of all allocations and research staff will not be able to see future allocations. The allocated group will be relayed back to delivery staff in the services who will decide which staff member, matching their allocated intervention or control group, a young person should be assigned to.

It is not possible to blind young people or staff to their allocated group although follow-up at months 6 and 12 will be conducted by researchers blind to allocation. Follow-up questionnaires are completed by participants and are the same for both groups, the questionnaires collect no details on what group the participant was allocated to.

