¹ The requirement of the funding means a report needs to be available by September 2025, this means the primary outcome is the 6-month version of the SRDS. As some interventions take longer than 6-months to deliver, a second report using SRDS at month 12 will also be produced later.

		
prosocial behaviour, externalising behaviours, internalising behaviours), psychological health, wellbeing, family cohesion, police involvement, school exclusions, suspensions, managed moves and employment status. At 6 and 12 months.
 
Staff Attitudes and perceptions towards trauma informed care, wellbeing, absence, turnover at 6 and 12 months

	
measure(s) (instrument, scale, source)
	
Participants Self-Reported Delinquency Scale (SRDS), Strengths and Difficulties Questionnaire (SDQ), General Health Questionnaire (GHQ12), Short Warwick Edinburgh Mental Wellbeing Scale (SWEMWBS), Brief Family Relationship Scale (BFRS), Client Service Receipt Inventory (CSRI)
 
Staff Attitudes related to Trauma Informed Care (ARTIC), Short Warwick Edinburgh Mental Wellbeing Scale (SWEMWBS), Staff records.

Baseline for primary outcome	variable	Quantity of self-reported delinquent acts in previous six months
	measure (instrument, scale, source)	Self-Reported Delinquency Scale (SRDS)
Baseline for secondary outcome	variable	
Participant Number of offences in the 6-months prior to baseline.
 
Self-report behaviour and personality attributes (overall behaviour, emotional symptoms, conduct problems, hyperactivity, peer relationships, prosocial behaviour, externalising behaviours, internalising behaviours) derived from the Strengths

		
and Difficulties Questionnaire, psychological health, wellbeing, family relationships at baseline.
 
Police involvement, school exclusions and suspensions, employment status over the past 6 months at baseline.
 
Staff
 
Attitudes and perceptions towards trauma informed care and wellbeing at baseline.
 
Days' absence and turnover over the past 6 months at baseline.

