To explore the proposed mechanism of change we will conduct a prognostic linear regression analysis to model the relationship between pre-randomisation factors; age, gender, ethnicity, IMD, SRDS, SDQ, BFRS, GHQ and observed outcomes at 6- and 12- months respectively on the primary outcome at either 6- or 12-months. Interaction terms with allocation arm will be included in the analysis, and a significance level of 0.1 will be used to determine which factors are to be included in the regression model. This analysis will be augmented by an additional

analysis including participants in the RBT arm only using the same pre-randomisation factors but also including process measures of compliance, therapeutic alliance, and interventionist attitude to trauma informed practice.

Interim analyses and stopping rules

No interim analyses are planned. The trial will only be stopped if evidence emerges of a serious adverse event associated with participation in the trial. As the intervention has already been implemented in practice with youth offending populations there is no evidence at the outset that a serious adverse event is likely to occur.

Longitudinal follow-up analyses

Assessments are conducted at baseline, prior to randomisation and then again at months 6 and 12, with 6-months being considered the primary endpoint. Table 2 provides an overview of what measures are being conducted at each time-point.

Outcome	No of items	Baseline	Six months	Twelve months
Primary				
Self-reported delinquency (SRDS) ¹	36	✓	✓	✓
Secondary				
Strength and Difficulties (SDQ) ¹	25	✓	✓	✓
Wellbeing (SWEBWMS)	7	✓	✓	✓
Psychological Distress (GHQ12)	12	✓	✓	✓
Family environment (BFRQ)	16	✓	✓	✓
Receipt Inventory (CSRI)	8	✓	✓	✓
Staff attitudes to trauma informed care (ARTIC)	35	✓	✓	✓
Staff wellbeing (SWEBWMS)	7	✓	✓	✓
Staff turnover & absence	2	✓	✓	✓
Exploratory				
Adverse childhood experiences (ACE-Q)	10	✓		
Process				
Therapeutic relationship	12		✓	
Proportion of sessions planned & delivered	1		✓	✓

Imbalance at baseline

Rather than just assume the randomisation has worked, we will assess observed balance by comparing the means and distributions of the groups created by randomisation for both participants and staff. If they are systematically different across those variables we observe – e.g. always larger / smaller in one group - then that would suggest the randomisation has not been successfully implemented. Baseline equivalence following randomisation will be

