assessed by first looking at allocation by the three stratifying variables, service, sex and age group for participants and service and specialism for staff.

Baseline characteristics will be summarised by allocated group. Summary measures for the baseline characteristics of each group will be presented as mean and standard deviation for continuous (approximate) normally distributed variables, medians and interquartile ranges for non-normally distributed variables, and frequencies and percentages for categorical variables. Following CONSORT when comparing intervention and control groups we will not employ statistical testing.

If there is a large imbalance between groups on a specific variable, then that variable will be included in the analysis model. If there are systematic differences across multiple variables that are indicative of failed randomisation then it would be necessary to explore alternative analysis methods to estimate intervention effects, such as instrumental variable models, using allocation as the IV.

Missing data

The proportion of missing data and patterns of missingness will be examined for the primary outcome only, quantity of offences at 6-month post-randomisation. Levels of missing data will be reported along with any systematic occurrences of missing data observed in the dataset.

In trials some participants are inevitably lost to follow-up. Sample size estimation assumed 10% of patients would not provide an evaluable 6-month follow-up assessment. We will explore the mechanism of missing data to establish whether the data can be considered missing completely at random or missing at random. For each arm we will present baseline data for those followed-up at 6 months and those lost to follow-up and logistic regression analysis to explore for any systematic differences between the allocated group. If no predictor variables emerge from the regression model then the missing data can be classed as missing at random.

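### The SAP reads baseline differences that all point one way as a sign of failed randomisation, but its baseline scales are correlated, so the pattern is weak evidence of failure

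*SAP*

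**What the plan says.** Under Imbalance at baseline, the SAP proposes to check whether randomisation worked by "comparing the means and distributions of the groups created by randomisation for both participants and staff". If the groups differ systematically, "e.g. always larger / smaller in one group - then that would suggest the randomisation has not been successfully implemented". The section sets no minimum difference, number of variables or scoring direction, and makes no allowance for correlation between variables. Nothing calibrates the pattern against chance: "Following CONSORT when comparing intervention and control groups we will not employ statistical testing".

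Two consequences follow. A large imbalance on one variable brings that variable into the model. Systematic differences over several variables that are "indicative of failed randomisation then it would be necessary to explore alternative analysis methods to estimate intervention effects" lead to other methods, "such as instrumental variable models, using allocation as the IV". The section does not say whether eq. 1 remains primary in that event.

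The SAP's Design overview lists as baseline scores for young people the SRDS, GHQ12, SWEMWBS, BFRS and eight SDQ scores: "overall behaviour, emotional symptoms, conduct problems, hyperactivity, peer relationships, prosocial behaviour, externalising behaviours, internalising behaviours". The Protocol (Secondary outcomes) says that the last two are multi-component scores generated from the SDQ.

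The Protocol (Randomisation) also states: "A full quality assurance AUDIT trail will be kept of all allocations". Both documents give each young person a unique identifier so that nobody is randomised twice (Protocol, Participants; SAP, Introduction).

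**The concern.** Agreement in direction over many variables is surprising only if the variables are close to independent. These are not. Most of the scales reflect how severe a young person's difficulties are, and the SDQ total, domains and composites share items. One chance difference in overall severity between the arms moves many of them together, and counting them separately counts that one difference several times.

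At stake is the reading of a sound trial. The team could report that randomisation had failed and bring in another estimation method, having made that judgement after seeing baseline data by arm. The criterion would also stand in for a direct check of the allocation process, which the Protocol already makes possible.

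**Working it through.** The documents state no false-alarm rate for this check and no correlation between scales, so there is no figure of the plan's to reproduce. The rates below rest on assumed inputs.

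**Inputs**
- Number of scales, k. All eight SDQ scores plus SRDS, GHQ12, SWEMWBS and BFRS give 12. Without the SDQ total and two composites there are 9. Splitting the BFRS into its three domains then gives 11. I use 8 to 12.
- Pairwise correlation, r: assumed to be 0.3 to 0.5 and equal for all pairs.
- Direction: scales scored so that worse is the same sign on each (assumed).
- Allocation 1:1, randomisation sound.

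**Formula.** Under sound randomisation, differences in means between arms have expectation zero and carry the correlations of the scales themselves. With equal correlation r, the chance that all k differences share a sign is

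P = 2 ∫ φ(u) Φ(−√r·u / √(1−r))^k du.

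Special cases: r = 0 gives 2 × (1/2)^k; r = 0.5 gives 2/(k+1). Sample size does not enter, so recruiting 562 does not lower the rate.

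**Results**

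| k | r = 0 | r = 0.2 | r = 0.3 | r = 0.4 | r = 0.5 |
|---|---|---|---|---|---|
| 8 | 0.8% | 6.1% | 10.4% | 15.8% | 22.2% |
| 9 | 0.4% | 4.7% | 8.6% | 13.8% | 20.0% |
| 11 | 0.1% | 2.9% | 6.2% | 10.8% | 16.7% |
| 12 | 0.05% | 2.4% | 5.3% | 9.7% | 15.4% |

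Hand check: k = 8, r = 0 gives 2/256 = 0.8%; k = 8, r = 0.5 gives 2/9 = 22.2%; k = 12, r = 0.5 gives 2/13 = 15.4%. The 5% to 22% range runs from k = 12, r = 0.3 to k = 8, r = 0.5.

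**Other readings, r = 0.3 to 0.5**
- Raw scoring direction, 2 of 8 scales reversed: 0.8% to 0.9%. With 3 of 12 reversed: below 0.1%.
- Three unrelated variables (demographics, say) must also agree, which multiplies the rate by (1/2)³: 10.4%/8 = 1.3% to 22.2%/8 = 2.8% for k = 8; 5.3%/8 = 0.7% to 15.4%/8 = 1.9% for k = 12.
- Every difference must also exceed 0.05 SD (k = 8, 562/2 = 281 per arm): 1.4% to 5.0%.
- One exception allowed: 29.7% to 44.4% for k = 8; 15.6% to 30.7% for k = 12.

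**Staff.** The check covers staff too. For ARTIC, SWEMWBS and absence with no correlation at all, the rate is 2 × (1/2)³ = 25%. With turnover as a fourth measure it is 2 × (1/2)⁴ = 12.5%. At zero correlation these two figures do not depend on scoring direction.

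**The case against.** The strongest reply is that there is no mechanical rule here. The same-direction pattern is offered as an example, it would only suggest a problem, and the later sentence asks for a further judgement. A criterion of that kind has no single false-alarm rate, so a reader who took 5% to 22% as a property of this trial would be going beyond the documents. That stands. It does not rescue the text, because the example is the SAP's only illustration of failed randomisation, and with neither test nor threshold the judgement would be formed on arm-level data.

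Second, the SAP speaks of larger and smaller, not worse, and of all observed variables, which include age, sex, ethnicity and IMD. Both readings lower the rate sharply, and that arithmetic stands. But on raw scoring the check loses its purpose: if more severe cases were steered to one arm, conduct problems would be larger there while prosocial behaviour and wellbeing would be smaller, and the pattern would not appear.

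Third, a reader might infer that the pattern removes the planned ANCOVA. The documents do not say so. The SAP says that alternatives are to be explored, Primary outcome analysis ties the primary analysis to the ITT dataset without condition, and the one alternative named, an instrumental variable model using allocation, is a framework already planned under Compliance. What remains is that the SAP does not say eq. 1 stays primary once failure is suspected, and its list of alternatives is open-ended. Whether that method could repair a failed randomisation is a separate question.

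Fourth, a reader might infer that the check cannot see real failures such as overridden allocations. That is too strong: overrides that steered severe cases to one arm would produce this pattern on severity-aligned scores. The check is non-specific rather than blind.

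**Conclusion.** The point holds as a faulty inference stated in the SAP, and one that should be corrected. Same-direction baseline differences are weak evidence of failed randomisation when the scales are correlated. The figure of about 5% to 22% is conditional on 8 to 12 severity-aligned scales and equal correlations of 0.3 to 0.5, none of which the documents state. Across the readings worked through, the rate runs from below 0.1% to about 44%; that spread shows how little the criterion fixes in advance. The 25% for three staff measures needs no assumed positive correlation, only that these three are the measures compared.

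The consequence is a possible one: a sound trial labelled as failed and a post hoc change of analysis prompted by it. The finding does not touch the validity of eq. 1, or the separate rule on a single imbalanced covariate.

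**What to change.** In the SAP, Imbalance at baseline:
- Remove the same-direction criterion, and the later sentence on systematic differences over several variables that relies on it.
- Judge whether randomisation was implemented correctly from the allocation audit trail and the unique identifiers: issued sequence against recorded arm, time order of consent, baseline and allocation, duplicate identifiers, and manual overrides. The audit-trail sentence stands in the Protocol's paragraph on young people, so say which record serves for staff.
- Report baseline tables descriptively for young people and staff.
- State that the eq. 1 ITT ANCOVA stays primary, and that any alternative model prompted by baseline patterns is a sensitivity analysis.

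Leave the single-covariate rule as it is. The cost is a short change of SAP text, best made before baseline data are tabulated by arm. For young people no new data are needed, since the audit trail and identifiers are already planned.

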We will assess intervention effects in the presence of non-compliance, with compliance measured at the individual level and including all those allocated as part of the trial. Our approach for assessing intervention effects under non-compliance will be via the instrumental variable framework (IV). The benefit of using an IV approach is that randomisation is maintained in the analysis, which is crucial for estimating unbiased intervention effects. In summary, with a binary measure of compliance CACE weights the analysis by treatment allocated (ITT) intervention effect by the proportion of compliers (eq. 5):

$$CACE = ITT / \textit{proportion compliant}$$

If the proportion compliant is 1.0 (i.e. perfect compliance) then the CACE estimate is the same as the ITT estimate, but otherwise the impact of this approach is to increase the magnitude of the intervention effect.

CACE uses a two-stage least squares (2SLS). The first stage model uses intervention received (T) as the outcome, with random allocation (Z) as the independent variable (eq. 6):

$$T = \alpha + Z$$

Based on the stage 1 model, we then calculate predicted values of intervention received (\hat{T}) for use in stage 2. The second stage model predicts the substantive outcome (Y e.g. quantity of offences) using the predicted values of intervention received (\hat{T}) based on the stage 1 model (Eq.7):

$$Y = \alpha + \hat{T} + \varepsilon$$

An additional sensitivity analysis will employ a per protocol approach (PP), containing all data for participants who complete the trial as planned – in intervention and control groups - without any major protocol violations or exclusions. PP analysis essentially drop those individuals who have not strictly complied with their allocation – both those who only partially complied with their allocated intervention and those who did not receive their allocated intervention. This means that PP represents a likely ‘best case scenario’ for intervention effect estimation. The PP dataset will be analysed in a similar manner to the ITT dataset.

Presentation of outcomes

As the sample is large, effect size differences will be calculated using Cohen’s d, specified in the following equation (eq. 8):

$$\delta = (Y_i - Y_o) / S$$

Where Y_i and Y_c are the regression adjusted means, derived from eq. 1, for the intervention and control groups respectively and S is the pooled standard deviation.

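### The only remedy the SAP names for failed randomisation, an IV model with allocation as instrument, depends on the randomisation having worked and would remove none of the bias

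*SAP*

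**What the plan says.** The SAP section "Imbalance at baseline" compares the groups formed by randomisation on observed variables: "Baseline characteristics will be summarised by allocated group". It gives as an example of failure a pattern that is "always larger / smaller in one group - then that would suggest the randomisation has not been successfully implemented".

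Two responses follow. A large imbalance on one specific variable leads to that variable being added to the model. The second response begins "If there are systematic differences across multiple variables that are indicative of failed randomisation"; in that case alternative methods would be explored, and the only one named is "such as instrumental variable models, using allocation as the IV". No significance test is used for the comparison, and no numerical threshold is given for either response.

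The SAP section "Compliance" explains why IV is used elsewhere in the plan: "The benefit of using an IV approach is that randomisation is maintained in the analysis, which is crucial for estimating unbiased intervention effects". Its eq. 5 sets CACE equal to ITT divided by the proportion compliant. Eqs. 6 and 7 give the two-stage form with allocation as the only first-stage predictor and no baseline covariates in either stage.

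**The concern.** IV with allocation as the instrument is a sound answer to non-compliance: people were allocated at random but did not all receive what they were allocated. It does not answer non-random allocation. The SAP's trigger is imbalance at baseline between the allocated groups. What happens after allocation cannot cause that, so the suspicion falls on allocation itself, which is the proposed instrument.

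If allocation really were compromised, an analyst following the example would report an estimate that looks repaired but carries all of the original confounding. The text also risks reading chance imbalance as failure. Baseline scales on the same young people are likely to be correlated, so differences that lean the same way are weak evidence that anything went wrong.

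**Working it through.** **1. The two SAP sections side by side**

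- Imbalance at baseline: IV is considered when the allocated groups differ systematically, read as failed randomisation.
- Compliance: IV is unbiased because randomisation is maintained.

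The condition that makes the method valid is the one the trigger says has failed.

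**2. Algebra from eq. 5**

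Let b be the bias in the ITT estimate and π the proportion compliant in the RBT arm. The SAP says control participants cannot access RBT, so π is the whole denominator.

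- Expected ITT estimate = true ITT + b.
- Expected IV estimate = (true ITT + b)/π = true CACE + b/π.
- Relative bias = (b/π)/(true ITT/π) = b/true ITT, the same as for ITT.

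At π = 1 the IV estimate equals the ITT estimate, as the SAP itself says.

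**3. Numbers**

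The documents give neither b nor an expected π. I assume b = 0.10 SD and show a range of π.

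| π | Bias on CACE scale, 0.10/π |
|---|---|
| 1.0 | 0.100 |
| 0.8 | 0.125 |
| 0.6 | 0.167 |
| 0.5 | 0.200 |
| 0.4 | 0.250 |

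Relative bias, for a true ITT effect of 0.25 SD: 0.10/0.25 = 40%. At π = 0.6 the true CACE is 0.25/0.6 = 0.417, and 0.167/0.417 is again 40%.

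**4. Simulation check**

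N = 506, the plan's follow-up target. That figure reproduces: effect size 0.25, two-sided alpha 0.05 and 80% power give 252.1, rounded up to 253 per arm. I ran 4,000 trials per row with zero true effect and a 0.2 SD imbalance in a prognostic factor correlated 0.5 with outcome, so b = 0.2 × 0.5 = 0.10.

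| π | Mean unadjusted ITT | Mean IV | Mean ITT adjusted for the factor | False positives, ITT | False positives, IV |
|---|---|---|---|---|---|
| 1.0 | 0.100 | 0.100 | 0.000 | 20.3% | 20.3% |
| 0.8 | 0.103 | 0.128 | 0.002 | 20.5% | 20.3% |
| 0.6 | 0.102 | 0.170 | 0.001 | 21.3% | 20.7% |
| 0.5 | 0.102 | 0.204 | 0.001 | 20.7% | 20.3% |

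Against a nominal 5%, IV and unadjusted ITT fail equally. Adjustment removes the bias here because the imbalanced factor is measured. It would not do so for an unmeasured one.

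**The case against.** **The sentence is only an illustration.** This stands. The SAP speaks of exploring methods and gives IV as an example. A reader might infer that IV would replace the primary estimate, or that a sound ITT result would be set aside. The documents do not say so: the primary analysis remains ITT under eq. 1, and nothing withdraws it.

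**Enlarging the bias is partly a change of scale.** This also stands. Dividing by compliance moves the target from ITT to CACE, so the relative bias and the test of no effect are essentially unchanged. It is tempting to set the 0.25 SD bias at 40% compliance against the plan's detectable effect of 0.25, but that effect is on the ITT scale. On the CACE scale it would be 0.25/0.4 = 0.625. The fair criticism is that IV fixes nothing.

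**The trigger may rarely be met.** The documents do not support a claim that it would fire often. With eight scales, an assumed common correlation of 0.3 to 0.5 and all scales keyed the same way, every difference shares a sign in 10.4% to 22.2% of properly randomised trials. But the battery mixes problem scales with positive ones such as wellbeing. With two of eight reverse-keyed (an assumption from the constructs), the figure is 0.8% to 0.9%. The same-direction pattern is also only an example, and the differences must further be judged indicative of failure. The protocol's allocation is online, independent, after baseline and concealed, so true failure is unlikely.

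**Failure might mean that people received the wrong arm.** IV would then be valid, but that cannot produce baseline differences between allocated groups, and CACE already covers it.

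**IV with covariates could help.** The covariates would then do the work, and eqs. 6 and 7 contain none. Eq. 1 already adjusts for baseline SRDS, sex, age group and service, so the bias left in the planned primary estimate could be smaller than the unadjusted figure used above.

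**Conclusion.** The point holds. The only remedy named for suspected failed randomisation relies on valid randomisation and would leave the bias in place. On the CACE scale the bias is b/π, which is 1.25 times b at 80% compliance and 1.67 times at 60%. Relative to the target effect it is unchanged, and the false-positive rate is not repaired (about 20% with and without IV in the simulated case).

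The logical conclusion needs no assumption beyond the SAP's own text. The sizes rest on an assumed ITT bias of 0.10 SD and assumed compliance, since the SAP gives no expected proportion. Its complier definition (trauma screening plus 80% of interventions offered) makes full compliance unlikely.

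Severity is minor: the sentence is contingent and exploratory, and the planned primary analysis is not altered by it.

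**What to change.** In the SAP section on imbalance at baseline:

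1. Delete the IV example, and reserve IV/CACE for non-compliance as already planned in the Compliance section.
2. State that eq. 1 stays primary whatever the baseline comparison shows.
3. State that suspected failure is investigated through the allocation audit trail that the protocol's Randomisation section already promises.
4. Add one sensitivity analysis that adjusts eq. 1 for all measured baseline variables, with the caveat that unmeasured imbalance cannot be corrected. This extends the rule the SAP already has for a single imbalanced variable.
5. State that same-direction differences on correlated baseline scales are not by themselves evidence of failure.

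The cost is a few sentences of SAP wording and one sensitivity model. No new data are needed.
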